8.4.9 Scheduled Visits

Refer to [Appendix 1](#): Schedule of Visits and Measurements for a schedule of visits and measurements.

8.4.10 Unscheduled Visits

Unscheduled visits can be performed in order to ensure subject safety. All procedures performed at an unscheduled visit will be recorded in the source documents and on the Unscheduled Visit eCRF. Any procedure indicated in the eCRF that is not performed should be indicated as “Not done.”

Evaluations that may be conducted at an Unscheduled Visit include:

- Blood Sampling for Immunogenicity Testing
- Slit-lamp Biomicroscopy
- Visual Acuity
- Intraocular Pressure
- Urine Pregnancy Test
- Dilated Fundoscopy
- Assessment of Adverse Events
- Assessment of concomitant medications and/or treatments and
- Any other assessments needed in the judgment of the investigator
- [Redacted]

8.4.11 Early Termination Visit

In the case when a subject discontinues from the study, every effort should be made by the site to conduct an early termination visit in order to monitor subject safety. All procedures performed at an early termination visit will be recorded in the source documents and on the Early Termination Visit eCRF.

- Study Drug Collection
- Monitoring and Query of AEs
- Record all Changes in Concomitant Medications
- Urine Pregnancy Test (for females of childbearing potential)
- Ora Calibra® Ocular Discomfort Scale
- Ora Calibra® Ocular Discomfort & 4-Symptom Questionnaire

- VAS
- OSDI[®]
- BCVA Utilizing an ETDRS Chart
- Slit-Lamp Biomicroscopy
- Conjunctival Redness
- TFBUT
- Corneal and Conjunctival Staining (fluorescein)
- Corneal and Conjunctival Staining (lissamine green)
- Schirmer's Test
- Intraocular Pressure
- Dilated Fundoscopy
- Blood Sampling for Immunogenicity Testing
- Any other assessments needed in the judgment of the investigator
- [REDACTED]

8.5 Compliance with Protocol

Subjects will be instructed on proper instillation and storage of study drug at the end of Visits 1, 2, 3, 4, and 5, and given written instructions. The subject's used and unused study drug vials will be collected at each visit from Visit 2 up to and including Visit 6 to assess dosing compliance. Dosing compliance will be based off the returned used and unused ampoule count. If the subject is less than 80% or more than 125% compliant with dosing based on the expected number of unused ampoules, then the subject will be deemed non-compliant, and a deviation should be recorded. If the subject is deemed non-compliant, the subject should be re-educated on IP compliance.

These guidelines will be used by the Investigator for determining the subject's necessary compliance for the study and for recording deviations from this compliance.

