11.5.1 Labeling/Packaging

Run-in and Investigational drug will be packaged and labeled into clinical kits.

For the run-in period, 17 pouches will be packaged in a 2-week clinical kit. Each pouch will contain 2 single-use ampoules to provide a sufficient medication supply for one day.

For the treatment period, 17 pouches will be packaged in a 2-week clinical kit. Each subject will receive 4 kits. Each pouch will contain 2 ampoules to provide a sufficient supply of randomized study drug for one day.

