7.2 Per Protocol (PP) Population

The PP population includes subjects in the ITT population who do not have significant protocol deviations. Protocol deviations will be assessed prior to database lock and unmasking. The PP population will be analyzed using observed data only for efficacy variables. Subjects in the PP population will be analyzed as treated.

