9.2 Protocol Deviations

The number and percentage of subjects with any, major, and minor protocol deviations will be summarized by treatment group for all randomized subjects. The number and percentage of subjects with any protocol deviation will also be summarized for the following categories: Informed Consent, Inclusion / Exclusion and Randomization, Test Article / Study Drug Instillation and Assignment at Site, Improper Protocol Procedures at Site, Site's Failure to Report Serious Adverse Event (SAE) / AE, Visit Out of Window, Subject's Non-compliance with Test Article, Subject's Use of Prohibited Concomitant Medication, Subject's Failure to Follow Instructions, and Other. A subject listing will be provided that includes the date, visit at which the deviation occurred (if applicable), deviation code, description of each deviation, whether the deviation was COVID-19 related, and the classification of whether the deviation was judged to be major or minor.

In addition, subject listings will be provided that include date of randomization, randomization number, randomization arm, actual treatment, and [REDACTED] whether inclusion and exclusion criteria were met, and inclusion in the analysis populations. A listing of subjects affected by COVID-19 discontinuations and protocol deviations will be generated as well.

A table summarizing the number of randomized subjects enrolled by site with percentages will be generated.

10. Demographic and Pretreatment Variables

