12.1 Dosing Compliance

Dosing compliance will be calculated as:

$$\text{Dosing Compliance (\%)} = (\text{Number of doses taken from Day 1 to study completion/discontinuation visit} / \text{Number of expected doses from Day 1 to study completion/discontinuation visit}) * 100$$

The number of doses taken will be calculated by subtracting the number of unused vials from the number of vials dispensed plus the total number of vials missed reported in the electronic case report form (eCRF). For subjects who do not receive a dose of randomized study drug, the number of expected doses will be 0 and compliance will be defined as 0. Otherwise, the number of expected doses will be calculated as $2 \times [\text{Date of Study Completion/Discontinuation} - \text{Date of Day 1} + 1]$. If a subject discontinues on Day 1 then the number of expected doses is 1.

Dosing compliance will be summarized using continuous descriptive statistics including mean, SD, median, minimum, and maximum for the Safety Population. Additionally, a categorical summary display frequencies and percentages of those deemed compliant, under-compliant (<80%), and over-compliant (>125%).

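### Protocol 8.5 names unused ampoules as the base for its 80%-125% compliance limits and gives no formula, which does not match the dose-based definition in SAP 12.1

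*Protocol*

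**What the plan says.** Protocol 8.5 begins with the data source: "Dosing compliance will be based off the returned used and unused ampoule count". It then sets the limits: "If the subject is less than 80% or more than 125% compliant with dosing based on the expected number of unused ampoules". Anyone outside these limits counts as non-compliant, which leads to a recorded deviation and re-education. No formula or worked example follows.

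SAP 12.1 does give a formula. Its numerator is "Number of doses taken from Day 1 to study completion/discontinuation visit", its denominator is the expected doses over the same period, and the same 80% and 125% cut-offs define under- and over-compliance. Unused vials enter only as a step towards doses taken.

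Protocol 11.5.1 fixes the supply: "For the treatment period, 17 pouches will be packaged in a 2-week clinical kit. Each subject will receive 4 kits". It adds: "Each pouch will contain 2 ampoules to provide a sufficient supply of randomized study drug for one day". Under Protocol 8.1.5 and 8.4.6, new kits are given at Visits 2, 4 and 5 (two at Visit 5), and the Visit 2 kit is handed back at Visit 3.

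SAP 9.2 has a deviation category "Subject's Non-compliance with Test Article". SAP 7.2 states: "The PP population includes subjects in the ITT population who do not have significant protocol deviations".

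**The concern.** Two documents use the same cut-offs on different stated bases. The only reference quantity named in the protocol sentence is the expected unused count. That count is the spare supply, not the doses due, so a percentage of it does not measure dosing. Its tolerance depends on how much reserve the subject holds at a given visit, and it moves in the wrong direction: a missed dose adds an unused ampoule and raises the figure.

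This is an operating rule. It decides who has a deviation recorded and who is re-educated, and up to 10 sites must apply it. Two sites could read the sentence differently and classify the same ampoule count in opposite ways. It is also the only numerical dosing limit that either document ties to a deviation, and neither says when a dosing deviation counts as significant for the PP set.

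**Working it through.** The documents state no expected unused count, so there is no figure of theirs to reproduce. The check is direct counting.

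**Inputs**
- Ampoules per kit: 17 pouches × 2 = 34 (Protocol 11.5.1). The Visit 5 supply is two kits, 68.
- Doses due: two per day from Day 1, with no home dose on the morning of a visit (Protocol 8.4.3 to 8.4.7). This gives 14 by Day 8, 28 for a 14-day kit, and 56 from Day 29 to Day 57.
- Assumptions: one ampoule per dose, the in-office dose taken from the kit, and visits on the planned day.

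**Formulas.** Let S be the supply, E the doses due, and m the doses missed (negative if extra doses are taken).
- Literal reading: unused / expected unused = (S − E + m) / (S − E) = 1 + m / (S − E). The subject passes if this lies between 0.80 and 1.25, so up to 0.25 × (S − E) missed and 0.20 × (S − E) extra doses are tolerated.
- Dose reading: taken / due = (E − m) / E, with the same limits.

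**Results, literal reading**

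| Count | S | E | Expected unused | Unused that pass | Doses that pass | % of doses due |
|---|---|---|---|---|---|---|
| Full kit, 14 days | 34 | 28 | 6 | 5-7 | 27-29 | 96.4%-103.6% |
| Visit 6 | 68 | 56 | 12 | 10-15 | 53-58 | 94.6%-103.6% |
| Visit 3, Day 8 | 34 | 14 | 20 | 16-25 | 9-18 | 64.3%-128.6% |

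- Full kit, 2 missed: 26/28 = 92.9% of doses; 8/6 = 133% of expected unused; flagged.
- Visit 6, 4 missed: 52/56 = 92.9%; 16/12 = 133%; flagged.
- Visit 3, 5 missed: 9/14 = 64.3%; 25/20 = 125%; passes.

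**Same counts, dose reading.** The first low flag comes at 6 missed of 28 (22/28 = 78.6%), 12 missed of 56 (44/56 = 78.6%) and 3 missed of 14 (11/14 = 78.6%). The two readings therefore disagree for 2-5 missed of 28 and 4-11 missed of 56 (flagged only by the literal reading), and for 3-5 missed of 14 at Visit 3 (flagged only by the dose reading).

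**Sensitivity, literal reading**
- Visit 3 on Day 7 (12 due, 22 unused expected): lowest pass is 7/12 = 58.3%. On Day 9 (16 due, 18 unused expected): 12/16 = 75.0%.
- Visit 3 with the in-office dose not from the kit (13 due): 8/13 = 61.5%.
- Single kit over 12 days: 22-26 of 24 doses pass (91.7%-108.3%). Over 16 days: only 32 of 32.
- Visit 4 counted for Days 8-15 only (20 left, 14 due, 6 unused expected): 13-15 doses pass. So 13/14 = 92.9% passes, and 12/14 = 85.7% is the first flagged.

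**The case against.** The strongest reply is that the literal reading is not the only one. The sentence just before the limits bases compliance on both used and unused ampoules, and the limits are attached to compliance with dosing. Unused ampoules can then be the data from which doses are worked out, as in SAP 12.1, and neither misclassification occurs. This stands: nothing in the documents shows that sites divide by the expected unused count. It does not remove the defect, because the sentence has no formula and the base it names points to the other reading.

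A reader might infer that the rule in general flags subjects at 93% of doses and passes subjects at 64%. The documents do not support that. The 64% pass arises only when a two-week kit is counted after one week at Visit 3. At a full-kit or Visit 6 count, 64% is flagged even on the literal reading (18/28 leaves 16 unused, 16/6 = 267%). The 93% flag also fails at Visit 4 if only the Days 8 to 15 supply named in Protocol 8.4.5 is counted.

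A reader might also infer that the efficacy conclusions are at risk. Both estimands ignore non-optimal compliance under a treatment-policy strategy in the ITT population. The PP analysis is supportive, and no text makes an ampoule-count deviation significant.

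Finally, SAP Section 1 says its methods supersede the protocol's. That covers statistical methods; it does not change how sites record deviations under 8.5. A visit-level flag and a whole-study percentage can also differ for one subject under any formula, so such a difference alone would prove nothing.

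**Conclusion.** The concern holds as a defect of wording in a rule that sites must apply. Protocol 8.5 names unused ampoules as the base, gives no formula, and does not match SAP 12.1. If it is applied literally on planned days, with one ampoule per dose, the passing range is about 95%-104% of doses for a full kit or the Visit 6 supply. At Visit 3 it is 64%-129%, with the lower limit moving from about 58% (Day 7) to 75% (Day 9). The percentage also runs opposite to dosing.

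The reach is limited to site deviation records, re-education and the non-compliance summary in SAP 9.2. The PP set is touched only if these deviations are judged significant. The ITT primary analysis and the SAP compliance table, which is built on doses, are unaffected.

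SAP 12.1 cannot simply be copied. As worded, it adds missed vials to doses taken. For a Day 57 exit it expects 2 × 57 = 114 doses, against 2 × 56 = 112 under the visit instructions.

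**What to change.** - In Protocol 8.5, state the percentage as doses taken (ampoules dispensed minus unused ampoules returned) divided by doses expected over the same counting interval, with the 80% and 125% limits applied to it. Say which interval applies at Visit 4 (Days 8 to 15, or the whole kit) and how unreturned ampoules are counted.
- Reconcile this with SAP 12.1, including the term that adds missed vials and the 114 against 112 expected doses.
- Before database lock and unmasking, re-derive the non-compliance deviations from the recorded ampoule counts on that basis, and use the result for the SAP 9.2 summary and any PP decision.

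The cost is a sentence in the protocol or a site memo, a small SAP edit, and one masked re-derivation from accountability data already collected. No new data are needed.

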8.6 Subject Disposition

8.6.1 Completed Subjects

A completed subject is one who has not been discontinued from the study.

8.6.2 Discontinued Subjects

Subjects may be discontinued prior to their completion of the study due to:

- pregnancy
- adverse events
- lack of efficacy
- unmasking when medically necessary

- protocol violations
- administrative reasons (e.g., inability to continue, lost to follow-up)
- sponsor termination of study
- subject choice (e.g. withdrawal of consent) and
- Any subject may be discontinued for any sound medical reason at the discretion of the investigator.

Notification of a subject discontinuation and the reason for discontinuation will be made to Ora and/or study sponsor and will be clearly documented on the eCRF.

Discontinued subjects will not be replaced.

8.7 Study Termination

The study may be stopped at an investigative site at any time by the IRB, regulatory authorities, investigator, the sponsor, and/or Ora with appropriate notification.

8.8 Study Duration

An individual subject's participation will involve at least 6 visits over approximately a 10-week (~70 days) period (56 days of treatment and 14 days pre-screening).

8.9 Monitoring and Quality Assurance

During the course of the study, a monitor, or designee, will make routine site visits to review protocol compliance, assess study drug/device accountability, and ensure the study is being conducted according to the pertinent regulatory requirements. The review of the subjects' medical records will be performed in a manner that adequately maintains subject confidentiality. Regulatory authorities of domestic and foreign agencies, quality assurance and or its designees may carry out on-site inspections and/or audits which may include source data check. Therefore, direct access to the original source data will be required for inspections and/or audits. All inspections and audits will be carried out giving consideration to data protection as well as subject confidentiality to the extent that local, state, and federal laws apply.

9 ADVERSE EVENTS

9.1 Adverse Events

An AE is defined as any untoward medical occurrence associated with the use of an IP in humans, whether or not considered IP-related. An AE can be any unfavorable and unintended sign (e.g., an abnormal laboratory finding), symptom, or disease temporally associated with the use of an IP, without any judgment about causality. An AE can arise from any use of the IP (e.g., off-label use, use in combination with another drug or medical device) and from any route of administration, formulation, or dose, including an overdose. An AE can arise from any delivery, implantation, or use of a medical device, including medical device failure, subject characteristics that may impact medical device performance (e.g., anatomical limitations), and therapeutic parameters (e.g., energy applied, sizing, dose release) associated with medical device.

All AEs spontaneously reported by the subject and/or in response to an open question from study personnel or revealed by observation, physical examination or other diagnostic procedures will be recorded in the source document and on the appropriate pages of the eCRF. Any clinically relevant deterioration in clinical finding is considered an AE and must be recorded. When possible, signs and symptoms indicating a common underlying pathology should be noted as 1 comprehensive event.

Documentation regarding the AE should be made as to the nature, date of onset, end date, severity, relationship to IP, action(s) taken, expectedness, seriousness, and outcome of any sign or symptom observed by the physician or reported by the subject upon indirect questioning.

If a female has a positive pregnancy test during the study, the investigator will notify Ora immediately (within 24 hours) via the Pregnancy Report Form and also report on the appropriate eCRF. Any subject found to be pregnant during the course of the study shall be discontinued from the study. The investigator shall request from the subject and/or the subject's physician copies of all related medical reports during the pregnancy and shall follow and document medical findings throughout the pregnancy through to the outcome of the pregnancy. The investigator will retain these reports together with the subject's source documents and will provide a copy of all documentation to Ora.

Note: A clinically significant visual acuity decrease (defined as an increase of 0.22 or greater in logMAR score) from baseline (Visit 2) will be considered an Adverse Event.

9.1.1 Reporting an Adverse Event of Special Interest

For all conjunctivitis (bacterial, viral, and hypersensitivity) AEs, the PI (or assigned study personnel) must complete a Conjunctivitis Adverse Events Reporting Instructions form. A copy of the form with a photo of the subject's eyes should be provided to Ora and the study sponsor within 72 hours of becoming aware of the event.

9.1.2 Severity

Severity of an AE is defined as a qualitative assessment of the degree of intensity of an AE as determined by the investigator or reported to him/her by the subject. The assessment of severity is made irrespective of relationship to IP or seriousness of the event and should be evaluated according to the following scale:

- *Mild*: Event is noticeable to the subject but is easily tolerated and does not interfere with the subject's daily activities.
- *Moderate*: Event is bothersome, possibly requiring additional therapy, and may interfere with the subject's daily activities.
- *Severe*: Event is intolerable, necessitates additional therapy or alteration of therapy, and interferes with the subject's daily activities.

9.1.3 Relationship to Investigational Product

The relationship of each AE to the IP is to be determined by the investigator using these explanations:

- ***Suspected***: A reasonable possibility exists that the IP caused the AE. A suspected AE can be further defined as:
 - *Definite*: Relationship exists when the AE follows a reasonable sequence from the time of IP administration, follows a known response pattern of the drug class, is confirmed by improvement on stopping the IP and no other reasonable cause exists.
 - *Probable*: Relationship exists when the AE follows a reasonable sequence from the time of IP administration, follows a known response pattern of the drug class, is confirmed by improvement on stopping the IP and the suspect IP is the most likely of all causes.
 - *Possible*: Relationship exists when the AE follows a reasonable sequence from the time of administration but could also have been produced by the subject's clinical state or by other drugs administered to the subject.
- ***Not Suspected***: A reasonable possibility does not exist that the IP caused the AE. A not suspected AE can further be defined as:
 - *Not Related*: Concurrent illness, concurrent medication, or other known cause is clearly responsible for the AE, the administration of the IP and the occurrence of the AE are not reasonably related in time, OR exposure to IP has not occurred.

Types of evidence that would suggest a causal relationship between the IP and the AE include: a single occurrence of an event that is uncommon and known to be strongly associated with IP exposure (e.g., angioedema, hepatic injury, Stevens-Johnson Syndrome); one or more occurrences of an event that is not commonly associated with IP exposure, but is otherwise uncommon in the population exposed to the IP (e.g., tendon rupture); an aggregate analysis of specific events observed in a clinical trial (such as known consequences of the underlying disease or condition under investigation or other events that commonly occur in the study population independent of drug therapy) that indicates those events occur more frequently in the IP-treatment group than in a concurrent or historical control group.

9.1.4 Expectedness

The expectedness of an AE should be determined based upon existing safety information about the IP using these explanations:

- *Unexpected*: an AE that is not listed in the IB or is not listed at the specificity or severity that has been observed
- *Expected*: an AE that is listed in the IB at the specificity and severity that has been observed
- *Not applicable*: an AE unrelated to the IP

AEs that are mentioned in the IB as occurring with a class of products or as anticipated from the pharmacological/ mechanical (or other) properties of the product but are not specifically mentioned as occurring with the particular product under investigation are to be considered unexpected.

The investigator should initially classify the expectedness of an AE. The Medical Monitor will review and determine the expectedness of all AE/SAEs following the investigator's assessment. The final classification of an AE is subject to the sponsor's determination.

9.2 Serious Adverse Events (SAE)

An AE is considered serious if, in the view of either the investigator or sponsor, it results in any of the following outcomes:

- Death
- A life-threatening AE
- Note: An AE is considered “life-threatening” if, in the view of either the investigator or sponsor, its occurrence places the subject at immediate risk of death. It does not include an AE that, had it occurred in a more severe form, might have caused death
- Inpatient hospitalization or prolongation of existing hospitalization
- Note: The term “inpatient hospitalization” refers to any inpatient admission (even if less than 24 hours). For chronic or long-term inpatients, inpatient admission includes transfer within the hospital to an acute/intensive care inpatient unit. Inpatient hospitalization does not include: Emergency room visits, outpatient, same day, and ambulatory procedures, observation and short stay units, rehabilitation facilities, hospice facilities, and nursing homes.
- Note: The term “prolongation of existing hospitalization” refers to any extension of an inpatient hospitalization beyond the stay anticipated or required for the reason for the initial admission as determined by the investigator or treating physician.
- A persistent or significant incapacity or substantial disruption of the ability to conduct normal life functions

- Note: An SAE specifically related to visual threat would be interpreted as any potential impairment or damage to the subject's eyes (e.g., hemorrhage, retinal detachment, central corneal ulcer or damage to the optic nerve).
- A congenital anomaly/birth defect

Important medical events that may not result in death, are life-threatening, or require hospitalization may be considered serious when, based upon appropriate medical judgment, they may jeopardize the subject and may require medical or surgical intervention to prevent one of the outcomes listed in this definition.

